1.0 General Information

***Please enter the full title of your study:**

Evaluate the use of omega-3 fortified smoothies to improve omega-3 index and physical performance related outcomes among Soldiers

***Please enter the Protocol Number you would like to use to reference the protocol:**

H2F Omega-3

* This field allows you to enter an abbreviated version of the Protocol Title to quickly identify this protocol.

Is this a multi-site study (i.e. Each site has their own Principal Investigator)?

No

Does this protocol involve the use of animals?

Yes No

4.0 Project Information

4.1 * What department(s) will be associated with this protocol?

Emergency Medicine

4.2 * Is the IRB of record for this study an IRB/HRPP that does NOT use EIRB? If Yes, complete the application according to the IRB/HRPP Determination.

If your Projects or Protocols are under the oversight of another IRB that does use EIRB, stop this submission and contact the core site and request an invitation as a performing site.

If your Project or Protocol is now being submitted for the first time to an IRB that does use EIRB, continue with this application and answer the questions to be reviewed by the IRB.

Answering yes means the board of record is an IRB that does NOT use EIRB.

Yes No

4.3 * Is this protocol research, expanded access, or humanitarian use device?

Yes No

4.4 * What type of protocol is this?

- Behavioral Research
- Biomedical Research
- Clinical trial (FDA regulated)

- Educational Research
- Expanded Access
- Humanitarian Use Device (HUD)
- Psychosocial Research
- Oral History
- Other

4.5 Are you conducting this project in pursuit of a personal degree?

Yes No

4.7 * Is this human subjects research? (As defined by 32 CFR 219) Human subject means a living individual about whom an investigator (whether professional or student) conducting research:

- (i) Obtains information or biospecimens through intervention or interaction with the individual, and uses, studies, or analyzes the information or biospecimens; or
- (ii) Obtains, uses, studies, analyzes or generates identifiable private information or identifiable biospecimens.

Yes No

4.8 * Do you believe this human subjects research is exempt from IRB review?

Yes No

8.3 Are there international sites?

Attach international approval documents, if applicable, when prompted. Note: Ensure local research context has been considered

Yes No

8.4 Is this an OCONUS (Outside Continental United States) study?

Yes No

Select the area of responsibility:

Have you obtained permission from that area of responsibility? (This is a requirement prior to study approval)

Yes No

9.0 Study Details

9.1 Key Words:

Provide up to 5 key words that identify the broad topic(s) of your study

Omega-3 fatty acids, Holistic Health and Fitness (H2F), Army Combat Fitness Test (ACFT), Performance, Nutrition

9.2 Background and Significance:

Include a literature review that describes in detail the rationale for conducting the study. Include descriptions of any preliminary studies and findings that led to the development of the protocol. The background section should clearly support the choice of study variables and explain the basis for the research questions and/or study hypotheses. This section establishes the relevance of the study and explains the applicability of its findings

Evidence suggests that mental [1-11] and physical [12-17] health are positively related to the omega-3 intake, and studies indicate that supplementation of omega-3 fatty acids may improve muscle recovery and range of motion while decreasing soreness and pain. [16, 18-21]

Omega-3 fatty acids are an essential part of the diet and are found primarily in marine-based sources of fatty fish including salmon, mackerel, and herring. The Omega-3 Index (O3I) is a reliable method used to measure omega-3 status, more specifically it represents the sum of eicosapentaenoic acid (EPA) and docosahexaenoic acid (DHA), as a percentage of red blood cells. Currently, O3I is the preferred method for assessing omega-3 status given its low biological variability and its ability to be measured in either the fed or fasted state. Generally, the O3I increases with greater consumption of marine-based omega-3; however, the extent varies by individual. Research indicates the general population and Service Members alike have a low O3I (~4%) and therefore at risk for poor health and suboptimal physical performance. [22] For optimal health, performance and a decreased risk for cardiovascular disease an O3I of $\geq 8\%$ is desirable.

The research utilizing the Omega-3 Index as a measure of omega-3 fatty acids began in relation to preventing severe cardiovascular risks. The research has expanded shows that omega-3 fatty acids can reduce triglyceride levels [23, 24] and may serve as an effective treatment option for cardiovascular disease, [12, 25] osteoporosis, [26, 27] psoriasis, [28] and arthritis. [29-32] Omega-3 fatty acids are thought to inhibit eicosanoids and inflammatory cytokines leading to analgesic effects. Additionally, preliminary studies support a rehabilitative role of omega-3 fatty acids in maintaining muscle mass and minimizing muscle wasting during a prolonged period of limb immobilization (i.e., leg cast). [33] Furthermore, O3I levels have been positively correlated with muscle protein synthesis and enhanced recovery from muscle damaging exercise (i.e. delayed onset muscle soreness), in both athletic and military populations. [16, 18-21]

Improving Service Members health and maintaining the ability to perform optimally are high priorities. An average O3I of ~4% is concerning. These findings, although not surprising given the lack of foods containing omega-3 fatty acids across military installations, require action. Innovative solutions to provide Service Members with omega-3 fatty acids are needed to achieve health and performance benefits. Therefore, the purpose of this study is to examine whether

increasing omega-3 fatty acid intake using a novel fortified food product improves performance and recovery outcomes in Holistic Health and Fitness (H2F) soldiers.

9.3 Objectives/Specific Aims/Research Questions:

Describe the purpose and objective(s) of the study, specific aims, and/or research questions /hypotheses

Objectives 1:

- Assess the impact of 8-weeks of daily consumption of 1600mg of omega-3 fortified smoothie on O3I response.

Objective 2:

- Determine the relationship between O3I and measures of performance and recovery.

We hypothesize regular consumption (one smoothie per day, five days per week, for eight weeks) of omega-3 enhanced smoothies (1600 mg omega-3 per smoothie) will increase O3I to 8% compared to a control group. We also hypothesize improvements in performance markers related to strength, flexibility, aerobic capacity and power as assessed by the Army Combat Fitness Test (ACFT), rate of perceived exertion (RPE), and recovery (a visual analog scale (VAS) for pain) in the intervention group compared to control. We hypothesize the control group will not reach an O3I of 8% and measures of performance and recovery will be statistically lower than in the intervention group.

9.4 Study Design:

Describe study design in one to two sentences (e.g., prospective, use of existing records/data /specimens, observational, cross-sectional, interventional, randomized, placebo-controlled, cohort, etc.). Specify the phase – Phase I, II, III, or IV – for FDA-regulated investigational drug research

A double blind randomized-placebo control trial will be conducted in collaboration with the Army Holistic Health and Fitness (H2F) Program. Participants will be randomly selected from two H2F training sites: Ft. Campbell and Ft. Drum. In total, 100 participants will be randomly selected, 50 per site. Each site will have 25 participants assigned to the placebo group and 25 participants assigned to the omega-3 enhanced smoothie group. All interested soldiers will enter their name. Participants will be randomly selected until 100 participants consent. Participants will be excluded if they have a fish allergy or if they are unable to complete an Army Combat Fitness Test (ACFT) for any reason. Participants taking omega-3 supplements will not be excluded, but will be instructed to be consistent for the duration of the study.

9.5 Target Population:

Describe the population to whom the study findings will be generalized

Soldiers

9.6 Benefit to the DoD:

State how this study will impact or be of benefit to the Department of Defense

Previous research already indicates omega-3 status is low in military personal. Increasing omega-3 fatty acid intake will not only help maintain a healthy force by minimizing chronic disease risks, if we determine omega-3 fatty acids improve performance or recovery, then guidelines can be developed and soldiers can be educated and the demand for these types of foods will lead the way in improving the military nutrition environment.

10.0

Study Procedures, Data Management, and Privacy

10.1 Study Procedures:

Describe step-by-step how the study will be conducted from beginning to end

This is an 8-week protocol with baseline and post-intervention data collections including: demographics, digitized questionnaires (nutrition, physical activity and sleep), O3I (collected by finger prick) and ACFT scores. We will assess changes in O3I status, performance on, and recovery from the ACFT at two H2F training sites (Ft. Campbell and Ft. Drum), after providing omega-3 enhanced or placebo smoothies. All smoothies will be pre-made, iso-caloric and provided in similar ready to drink containers. Researchers and participants will be blinded, one staff member will not be blinded and maintain the key identifying which participants receive the placebo vs intervention. A smoothie log based on participant ID will be coded (i.e., A or B) to assist in distribution of the smoothies. Each smoothie will have a lot number that ends in A or B.

Baseline visit: To account for potential confounding factors, dietary intake assessed using the Health Eating Score (HES), daily physical activity using the Physical Activity Questionnaire (PAQ), and sleep using the Pittsburg Sleep Quality Index (PSQI) sleep questionnaire will be collected using REDCap. O3I will be collected by finger prick. A baseline ACFT will be conducted by trained Army staff (not researchers). The ACFT scores will be reported to the researchers by the participants. Participants will log into REDCap to report their ACFT score and report the Rate of Perceived Exertion (RPE), a score of 6-20 and the pain score, ranging from 0-10. This will be recorded one hour and 24 hour post ACFT.

Intervention: To ensure compliance, participants will be provided an omega-3 smoothie or placebo daily (Monday-Friday) by brigade dietitians or assigned staff immediately following training.

Post-Intervention data collection: After eight weeks of intervention O3I, questionnaires and ACFT scores will be collected again with participants reporting their RPE and pain scores following the same format as the baseline visit.

Participants will be given a USU-approved tablet to complete a digitalized participant's questionnaire, utilizing a USU-secure web based platform such as REDCap or will be emailed an anonymous survey link. Using this link, they will access REDCap to complete the questionnaires on their laptop or phone. No personally identifiable information nor personal health information will be recorded in the questionnaires. Methods to complete the questionnaire are outlined below:

1. Use a USU-approved tablet to complete the questionnaire using the USU REDCap capabilities.
2. Use their personal phone or laptop to complete the questionnaire using the USU REDCap capabilities.
 1. Research staff will email them two options to access questionnaire via REDCap
 1. Website link with an accompanying Access Code
 2. QR code to access the electronic consent documents
 3. Paper questionnaires will be available in case there are technical issues.

10.2 Data Collection:

Describe all the data variables, information to be collected, the source of the data, and how the data will be operationally measured.

Omega-3 Index This requires a finger prick with a lancet, similar to how a person with diabetes would check their blood sugar levels. This method will be used to obtain 1-2 drops of blood that will be placed on the provided collection card and sent to OmegaQuant to determine the Omega-3 Index.

Procedures for participants The Omega-3 kit include an alcohol pad to clean the finger, a blood collection card, a lancet, gauze and bandage. Instructions are included. Researchers will be assisting with the finger pricks.

Participants are instructed to: 1. Wash their hands with warm water, hold their arm down at their side for 20 seconds. 2. Use the alcohol pad to clean the index, middle or ring finger and remove any excess liquid with the gauze. 3. Twist off the blue plastic lancet cover. Place the lancet lightly on the side of the finger. Press down firmly onto the finger until you hear a click. Allow a drop of blood to collect on the finger. Lightly squeeze if needed. Then lightly touch the drop of blood to the dotted circle on the blood collection card. Completely fill the circle with blood. 4. When finished, apply pressure to the figure with the gauze pad and apply adhesive bandage. 5. Let the blood spot dry for 15-20 minutes then fold the collection card flap and place the card in the plastic bag. 6. Dispose of all materials in the trash.

Army Combat Fitness Test (ACFT) This is the standard fitness test for the soldiers. An ACFT will be conducted by trained staff at week 1 of the study and week 8. These will be standard practice ACFTs for the entire company (not only those in research).

Rate of Perceived Exertion (RPE) Immediately after the ACFT participants will be asked on a scale of 6-20 the how hard they were working during the ACFT.

Defense and Veterans Pain Scale Participants will report their pain score one hour and twenty four hours after each ACFT. Participants are shown a scale ranging from 0-10 with the picture of a face and a description that best matches how they feel.

Healthy Eating Score (HES) On the demographics questionnaire we also include 8 healthy eating questions. This will allow us to assess if there were any changes in diet throughout the duration of the study, and captures fish intake.

Diet ID An electronic method of capturing dietary intake that provides a complete picture of nutrient intake. Here is a product demo video: <https://vimeo.com/665298627>

Pittsburgh Sleep Quality Index (PSQI) PSQI will be utilized to qualitatively assess participants' sleep quality. The PSQI is a 19-item questionnaire that calculates sleep quality over the past month and assesses the following dimensions: sleep quality, sleep latency, sleep duration, habitual sleep efficiency, sleep disturbances, use of sleep medication, and daytime dysfunction. The PSQI generates a global score ranging from 0 – 21 with higher scores demonstrating worse sleep quality. Scores higher than 5 reflect poor sleep quality (clinical insomnia). The instrument takes 5 – 10 minutes to complete. It has been used in various populations. A global PSQI score > 5 yielded a diagnostic sensitivity of 89.6% and specificity of 86.5% (kappa = 0.75, p < 0.001) in distinguishing good (healthy subjects) from poor sleep.

Physical Activity Questionnaire (PAQ) The Physical Activity Questionnaire is an 8-item scale to assess weekly exercise patterns.

Participants will be given a USU-approved tablet to complete a digitalized participant's questionnaire, utilizing a USU-secure web based platform such as REDCap or will be emailed an anonymous survey link. Using this link, they will access REDCap to complete the questionnaires on their laptop or phone. No personally identifiable information nor personal health information will be recorded in the questionnaires. Methods to complete the questionnaire are outlined below:

1. Use a USU-approved tablet to complete the questionnaire using the USU REDCap capabilities.
2. Use their personal phone or laptop to complete the questionnaire using the USU REDCap capabilities.
 1. Research staff will email them two options to access questionnaire via REDCap
 1. Website link with an accompanying Access Code
 2. QR code to access the electronic consent documents
 3. Paper questionnaires will be available in case there are technical issues.

10.3 At any point in the study, will you request, use, or access health information in any form, including verbal, hard copy and electronic?

Yes No

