11.0 Statistical/Data Analysis Plan

11.1 Statistical Considerations:

List the statistical methods to be used to address the primary and secondary objectives, specific aims, and/or research hypotheses. Explain how missing data and outliers will be handled in the analysis. The analysis plan should be consistent with the study objectives. Include any sub-group analyses (e.g., gender or age group). Specify statistical methods and variables for each analysis. Describe how confounding variables will be controlled in the data analysis

We plan to analyze results using multiple regression analysis whereby we will regress outcomes (O3I, ACFT scores) onto treatment-allocation, controlling for pre-treatment factors (e.g., pre-O3I, demographics). This is equivalent to a two-group ANCOVA. For most analyses, we aim to keep outcomes continuous. In sensitivity analyses, we will also dichotomize O3I (e.g., at 8%, which is the cutoff for healthy O3I), examine mixed generalized linear models, and examine the design-effect of each site (which may decrease power somewhat). Alternative model specifications or variable-transformations will be considered in cases where gross violations invalidate certain approaches.

11.2 Sample Size:

80-100 participants

11.3 Total number of subjects requested (including records and specimens):

100

11.4 If you are recruiting by study arm, please identify the arms of the study and how many subjects will be enrolled in each arm

N/A

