11.5 Please provide a justification for your sample size

Power calculations, performed using the pwr2ppl package in r (<https://www.routledge.com/Applied-Power-Analysis-for-the-Behavioral-Sciences-2nd-Edition/Aberson/p/book/9781138044593>), were executed based on the expected associations between treatment allocation (i.e., treatment vs control) and the outcome variables (post-O3I, ACFT scores), controlling for baseline statuses (e.g., pre-O3I). We also assumed there would 20% be missing data or attrition, and that baseline statuses would not be associated with treatment allocation. Alpha was set alpha at 0.05 and power at 0.8. Under these conditions, with an analytic sample size of 80 subjects, and assuming a correlation between pre- and post-O3I (or pre- and post-ACFT score) of 0.6, the study will be adequately powered to detect an association of $r = 0.25$ between treatment allocation and the outcome. This converts into a cohen's d (or standardized-unit difference) of 0.55. This is generally considered a moderate-to-strong effect size. Based on previous research examining distribution and change in O3-I in similar samples, this would likely be equivalent to a treatment-effect of 0.6%-unit increase in O3-I. If there is a weaker association between pre- and post-O3I (or other outcomes), then the minimal detectable effect size would increase (e.g., if the pre/post association is 0.4, then the minimal detectable effect would be a Cohen's d of 0.6); if there is a stronger association between pre- and post-O3I, then the minimal detectable effect size would decrease (e.g., if the pre/post association is 0.8, then the minimal detectable effect would be a Cohen's d of 0.4).

11.6 Data Analysis Plan: Complete description: Background, Objectives, Design, Step by Step how the project is going to be done, Data analysis plan:

In addition to the analyses indicated in 11.1, additional measures will be undertaken to ensure that data are of high-quality over the course of the study, including double data entry where relevant, periodic inspection of data as it is collected, and periodic preliminary analyses. Statistical packages to be used will primarily include Microsoft Office Excel and IBM SPSS.

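### The intended guideline claim on performance or recovery rests on four to eight outcomes with no primary outcome and no multiplicity control; a false claim of improvement is about 8–18% likely under no effect

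*Combined protocol and SAP*

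**What the plan says.** - **Intended use (9.6).** "if we determine omega-3 fatty acids improve performance or recovery, then guidelines can be developed". Either side of the disjunction is enough on this wording.
- **Hypotheses (9.3).** Better results are expected on "strength, flexibility, aerobic capacity and power as assessed by the Army Combat Fitness Test", on RPE and on pain. The section expects a statistical difference between groups on performance and recovery.
- **ACFT variable (10.1).** "Participants will log into REDCap to report their ACFT score". The word is singular, and no section says whether the analysis uses a total, event scores or domain scores.
- **Pain (10.2).** "Participants will report their pain score one hour and twenty four hours after each ACFT".
- **RPE.** Section 10.2 has it once: "Immediately after the ACFT participants will be asked on a scale of 6-20". Section 10.1 mentions RPE and pain together and then gives one hour and 24 hours as the recording times, which can be read as covering both.
- **Analysis (11.1).** The model will "regress outcomes (O3I, ACFT scores) onto treatment-allocation", adjusted for baseline. RPE and pain are not named. No outcome is called primary.
- **Error rate (11.5).** "Alpha was set alpha at 0.05 and power at 0.8". The sample size is justified for post-O3I and for ACFT scores alike. No sidedness, alpha split, hierarchy or adjustment is given.

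**The concern.** The 0.05 in 11.5 is the error rate of one test. The claim in 9.6 can be reached through any of several tests, and the plan does not fix how many. A single chance result on, say, one ACFT domain or one pain time point could be reported as a benefit and carried into Army nutrition guidance, and nothing in 11.1 would count against that. The recovery half of the claim is the weakest part: 11.1 specifies no analysis for it, so the choice of time point and model is open until the data are seen.

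**Working it through.** **1. The plan's own figure.** Inputs from 11.5: analytic N = 80, r = 0.25 between allocation and outcome, pre/post correlation 0.6, alpha 0.05 (taken as two-sided), power 0.8.

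- f² = r² / (1 − r² − 0.6²) = 0.0625 / 0.5775 = 0.108
- F-test with 1 and 77 degrees of freedom, noncentrality 0.108 × 77 = 8.33: power = 0.813
- 80 / (1 − 0.20) = 100 enrolled, as in 11.3

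The sample size therefore reproduces, for one test at 0.05. The smallest d detectable with 80% power on the same formula is 0.51. The stated 0.55 is slightly conservative.

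**2. Number of tests behind performance or recovery (O3I not counted).**

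- Four: one ACFT score, RPE once, pain at 1 h and 24 h
- Seven: four ACFT domains, RPE once, pain at 1 h and 24 h
- Eight: four ACFT domains, RPE at two times, pain at two times

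**3. Chance of a false result under no effect.** The documents state neither sidedness nor correlation between outcomes. I assume two-sided 0.05, so 0.025 in the favourable direction, and equal correlation from 0 to 0.5. For independent tests:

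- any significant difference, either direction: 1 − 0.95^k
- at least one false improvement: 1 − 0.975^k

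For k = 7 these give 1 − 0.95^7 = 0.302 and 1 − 0.975^7 = 0.162. The values at correlation 0.5 come from simulating equicorrelated normal test statistics (1,000,000 draws).

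| Tests | False improvement, corr. 0 | corr. 0.5 | Any difference, corr. 0 | corr. 0.5 |
|---|---|---|---|---|
| 1 | 2.5% | 2.5% | 5.0% | 5.0% |
| 4 | 9.6% | 7.8% | 18.5% | 15.6% |
| 7 | 16.2% | 11.5% | 30.2% | 23.0% |
| 8 | 18.3% | 12.5% | 33.7% | 25.0% |

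Even the smallest false-improvement figure, 7.8%, is about three times 2.5%. If each test were one-sided at 0.05, seven tests would give 30.2% at correlation 0 and 20.4% at 0.5, but the plan does not say its tests are one-sided.

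**4. Two prespecified tests with Holm.** The smaller p-value is compared with 0.025.

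- Any false rejection under no effect, independent tests: 1 − 0.975² = 4.9%
- False improvement, independent tests: about 1 − 0.9875² = 2.5%
- Detectable d at alpha 0.025, same formula as step 1: 0.56, against 0.51 at 0.05

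**The case against.** **Section 9.6 is not a decision rule.** It answers a form field on benefit to the Department of Defense, says only that guidelines can follow, and does not say that one significant p-value is enough. Elsewhere, the purpose statement and the hypothesis join performance and recovery with *and*. This stands: a reader might infer a formal any-one-significant rule, and the documents do not contain one. What remains is that 9.6 is the protocol's own account of how results will be used, and 11.1 sets no limit on it.

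**The number of tests is not in the plan.** Section 11.1 names only O3I and ACFT scores, and 10.1 speaks of one score. This also stands. A reader might infer at least seven tests from the four domains in 9.3, but seven is one reading between four and eight. That the plan leaves this range open is part of the problem.

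**The either-direction error is the wrong measure.** A reader might take 23–30%, the seven-test figure, as the chance of a false claim. It counts results in which the smoothie group does worse, and those cannot support a claim of improvement. The relevant seven-test figure is 11.5–16.2%.

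**O3I as a gatekeeper would not help much.** The stated purpose is performance and recovery, the study is sized for both O3I and ACFT, and the plan expects O3I to rise, so such a gate would seldom close. I agree and do not propose one.

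**Conclusion.** The point holds as a gap worth closing. The plan has no primary outcome and no multiplicity control for a claim that can be reached through several outcomes. Under no effect, a false improvement is about 8–18% likely across four to eight tests, against 2.5% for one. The chance of any significant difference is about 16–34%.

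These figures rest on two-sided 0.05 tests and equal between-outcome correlation of 0 to 0.5, both assumed. Higher correlation would lower them: at 0.8, seven tests give a false improvement of 7.5%. They leave out the further freedom in 11.1 and 11.6 (covariates given only as examples, alternative model specifications, periodic preliminary analyses), which I have not quantified. The sample-size calculation is not in question.

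**What to change.** Add a paragraph to 11.1:

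- **Objective 1:** week-8 O3I, by ANCOVA on baseline O3I, is the primary outcome at two-sided 0.05.
- **Performance or recovery claim:** name one performance variable (for example a single overall ACFT score, defined in the plan) and one recovery variable (one pain time point, chosen by the investigators in advance). Adjust each for its baseline value and test the two with Holm at two-sided 0.05, whatever the O3I result.
- **Everything else:** report ACFT domains, RPE, the other pain time point and the 8% O3I cut-off with confidence intervals as exploratory, and state that the 9.6 claim will not rest on them.
- **RPE timing:** reconcile 10.1 with 10.2, so that the list of outcomes is fixed.

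The cost is text only, with no new data or participants. O3I keeps its full alpha. At the stricter Holm step the detectable d for the two claim tests rises from about 0.51 to 0.56, close to the 0.55 already stated in 11.5. Single ACFT domains could no longer carry a claim. The analysis of Objective 2, the association between O3I and the other measures, is a separate question that this paragraph does not settle.

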12.4 Special categories, check all that apply

- Minors /Children
- Students
- Employees - Civilian
- Employees - Contractor
- Resident/trainee
- Cadets /Midshipmen
- Active Duty Military Personnel
- Wounded Warriors
- Economically Disadvantaged Persons
- Educationally Disadvantaged Persons
- Physically Challenged (Physical challenges include visual and/or auditory impairment)
- Persons with Impaired Decisional Capacity
- Prisoners
- Pregnant Women, Fetuses, and Neonates
- Non-English Speakers
- International Research involving Foreign Nationals - Headquarters Review is necessary

You must also consider the requirements of DoDI 3216.02, Enclosure 3, paragraph 7.e.

12.5 Inclusion Criteria:

Order Number	Criteria
1	Current soldier at Ft. Drum or Ft. Campbell.
2	Able and willing to complete two Army Combat Fitness Test (ACFT) (Week 1 and week 8)
3	Willing to obtain two finger pricks for the Omega-3 Index (week 1 and week 8)

12.6 Exclusion Criteria:

Order Number	Criteria
1	Allergic to fish

13.0

Recruitment and Consent

13.1 Please describe the recruitment process, including how subjects will be identified and selected for the study.

Recruiting

Recruitment will be done by briefing select companies where command has approved the soldiers to participate (See recruitment brief). Volunteers who are interested and meet the eligibility criteria will provide their name and email address. Once recruitment has ended participants will be randomly selected to participate and notified by email. Participants selected will review the eICD with researchers. Once all 100 participants are selected and have signed the electronic informed consent (eICD) they will be allocated to either the intervention (smoothie enhanced with omega-3) or placebo (smoothie with no omega3) group.

13.2 Compensation for Participation:

N/A

13.3 Please describe the pre-screening process. If no pre-screening, enter Not Applicable in the text editor

N/A

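### The ACFT is a whole-company test, but allocation is balanced only by site and the model does not name company; if a site supplies several companies, this costs a little precision that stratified allocation would recover

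*Combined protocol and SAP*

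**What the plan says.** Section 10.2 places the ACFT at weeks 1 and 8 and describes it as a routine unit test: "These will be standard practice ACFTs for the entire company (not only those in research". Section 10.1 adds, for the first of them: "A baseline ACFT will be conducted by trained Army staff (not researchers". RPE and pain are reported after the same tests.

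On recruitment, section 13.1 states: "Recruitment will be done by briefing select companies where command has approved the soldiers to participate". It does not say how many companies there are at either site.

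On allocation, section 9.4 states: "Each site will have 25 participants assigned to the placebo group and 25 participants assigned to the omega-3 enhanced smoothie group". Section 13.1 gives the order of events: "Once all 100 participants are selected and have signed the electronic informed consent (eICD) they will be allocated". Neither section mentions company as a balancing factor.

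On analysis, section 11.1 says: "we will regress outcomes (O3I, ACFT scores) onto treatment-allocation, controlling for pre-treatment factors (e.g., pre-O3I, demographics". Among the sensitivity analyses it will "examine mixed generalized linear models, and examine the design-effect of each site (which may decrease power somewhat". Site is the only grouping named, and the mixed models have no stated grouping factor. The sample-size section (11.5) allows for no clustering.

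**The concern.** If a company is tested as a unit, its members probably share the week-8 test occasion and may share graders and the training of the preceding eight weeks. Adjusting for baseline ACFT removes much of any stable difference between companies. It cannot remove what happens to a company between the two tests or on the second test day. RPE and pain, reported after the same test, are exposed in the same way.

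Adjusting for site does not help when one site supplies several companies. Their differences then go into the residual of the ACFT comparison. Because the arms are balanced only by site, a company can also contribute more soldiers to one arm than to the other. These are not two separate harms: uneven splitting is the route by which company variance enters the standard error of the treatment effect. What is at stake is interval width and power for the performance outcomes.

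**Working it through.** **Inputs from the plan (11.5, 9.4):** 80 analysed (40 per arm), r = 0.25, pre/post correlation 0.6, alpha 0.05 (two-sided assumed), power 0.80, 20% loss, 25:25 within each of two sites.

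**Assumptions, because the documents give no figures:** company explains 5%, 10% or 20% of residual ACFT variance (written ICC below), with one, two or four companies per site.

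**1. The plan's own figure.** With treatment uncorrelated with baseline, f² = r²/(1 − r² − 0.6²) = 0.0625/0.5775 = 0.108. The noncentral F test on 1 and 77 degrees of freedom gives power 0.813, and 80/0.8 = 100 enrolled. The stated 80% reproduces. As a standardised difference, r = 0.25 is d = 2 × 0.25/√(1 − 0.0625) = 0.516. The plan prints 0.55; the gap does not affect this point, and I use 0.516.

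**2. How unevenly companies can split.** Take two companies of 25 at a site, with 25 of the 50 soldiers drawn into each arm. The hypergeometric SD of one company's count in an arm is √(25 × ½ × ½ × 25/49) = 1.79. The arm difference in that company's share therefore has SD 2 × 1.79/25 = 0.143, or 14 percentage points. A split of 15–10 or worse has probability 0.26. A company supplying 12 of 50 splits 8–4 or worse with probability 0.32.

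**3. What that does to the outcome.** Residual variance after baseline adjustment is 1 − 0.6² = 0.64, so the company SD is √(0.64 × ICC). Within a site, the chance arm difference is 0.143 times the gap between its two companies, which has SD √2 × company SD. Averaging two sites divides by √2, leaving 0.143 × company SD.

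| ICC | Company SD | Typical (1 SD) arm difference |
|---|---|---|
| 0.05 | 0.179 | 0.03 |
| 0.10 | 0.253 | 0.04 |
| 0.20 | 0.358 | 0.05 |

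Simulation with 80 analysed (4,000 trials per setting) gives slightly larger 1 SD values: up to 0.06 with two companies per site and 0.07 with four. The 95th percentile is 0.06–0.12 SD with two and 0.07–0.14 SD with four, against a target of about 0.52–0.55 SD.

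**4. Validity.** In the same simulation with no treatment effect, leaving company out gave rejection rates of 0.045–0.050 for ICC 0.05–0.20 and two or four companies per site. The mean estimate stayed within 0.003 of zero.

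**5. Power at d = 0.516, allocation balanced by site only.** Each cell is power without company / with company as a fixed effect.

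| ICC | Two per site | Four per site |
|---|---|---|
| 0 | 0.80 / 0.79 | 0.82 / 0.78 |
| 0.05 | 0.81 / 0.81 | 0.82 / 0.80 |
| 0.10 | 0.83 / 0.84 | 0.81 / 0.81 |
| 0.20 | 0.83 / 0.87 | 0.81 / 0.85 |

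Adjustment alone can therefore lose up to about 4 points when company does not matter.

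**6. Balancing plus adjusting.** If balance survives among those analysed, four per site gives 0.82, 0.83, 0.84 and 0.89 at ICC 0, 0.05, 0.10 and 0.20. With 20% lost at random after a balanced allocation, and site in the comparison model, the gain shrinks to about 0 to 5 points for ICC 0.05–0.20. The loss is up to about 2 points at ICC 0 with four per site.

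**7. If company variance is additional.** The steps above treat company variance as already inside the 0.6 correlation. If it comes on top and is left in the error, power falls from 0.82 to about 0.80, 0.78 and 0.73 at ICC 0.05, 0.10 and 0.20.

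**The case against.** The premise is partly inferred. The documents describe testing by company, but they do not say that test days, graders or training differ between companies, or how many companies each site supplies. A plural across two sites is compatible with one company at each. The 25:25 site split would then balance company exactly. This stands, and it makes the point conditional.

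A reader might also go further than the text allows in four ways.

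- **That company confounds the treatment comparison or invalidates the tests.** It does not. Soldiers are allocated individually within site, so any imbalance is chance and is already reflected in the standard error (step 4).
- **That the plan excludes company.** It does not. The covariate list in 11.1 is open, mixed models and alternative specifications are allowed, and the demographics questionnaire is not itemised, so unit may even be recorded. Company is uncommitted rather than ruled out. However, an open list does not secure the adjustment, and it cannot supply balance after allocation.
- **That adding company guarantees a gain.** It does not. Removing all company variance with perfect balance would take power from 0.81 to 0.83–0.87 at ICC 0.05–0.15, but the planned 20% loss erodes that balance, and fixed effects without balancing can cost power.
- **That these are the outcomes with least power.** Section 11.5 applies the same assumptions to O3I and ACFT and gives none for RPE or pain, so the documents do not support a ranking.

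**Conclusion.** The point holds as a conditional, minor matter of efficiency. Testing is by company, balance is by site, and nothing in the plan commits to using company. If at least one site supplies more than one company, and if company explains 5–20% of residual ACFT variance, the plan gives up about 0 to 5 power points and accepts an avoidable typical arm difference of about 0.03–0.05 SD (two equal companies per site). Both conditions are assumptions. If each site supplies one company, the point disappears. The validity of the planned comparison is not in question.

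It is still worth raising because all 100 soldiers consent before anyone is allocated, so balancing is easy then and impossible afterwards.

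**What to change.** Record company at consent. Before allocation, build the list so that each company is split as evenly as possible between arms while the 25:25 totals at each site are kept. Stratified allocation should come first; adjustment should follow it rather than replace it.

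Then name the same factor, company within site, in section 11.1 for the ACFT analysis and for any RPE or pain analysis (11.1 currently specifies none). Fit it as a random effect, or as a fixed effect with small companies pooled by a rule written down before allocation, so that pooling is not an analyst's later choice. If each site turns out to supply a single company, say so; no change is then needed.

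The cost is one data field and a blocked list, with no extra participants or visits. The downside is up to about 2 power points if company proves irrelevant and there are several per site.
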